10 SAFETY ANALYSES

10.1 Adverse events

All Adverse Events (AEs) occurring during the study (ie, after signature of the informed consent document) will be recorded in the eCRF and reported using the SS.

For each AE the following information will be recorded in the eCRF: AE term (verbatim term), date of onset, whether or not the AE was an infusion reaction, if yes, whether this infusion reaction fulfills the Sampson criteria (for the definition of Sampson criteria, see Sampson et al, 2006), pattern of event, whether or not the AE was classified as a SAE or as an AE of special interest or special monitoring, intensity, relationship to concomitant medications, relationship to the investigational medicinal product (IMP), action taken with IMP, other action taken, outcome, date of outcome and whether the AE led to study premature termination. All AE data will be listed.

AEs are characterized as either pre-treatment or treatment-emergent according to the following criteria:

- Pre-treatment AEs are the events with onset date prior to the first administration of study medication (DZP or PBO).
- Treatment-emergent AEs are those with onset date on or after the first administration of study drug, and up to 60 days after last dose. The events that emerge after the final drug administration up to 60 days after last dose, will therefore also be considered as treatment-emergent even if recorded during the SFU period.

Time to onset of AE (noted as “Days Since First Dose” on AE listings) is calculated as the time (in days) between first dose and onset of AE. Time to onset of AE is not calculated for pre-treatment AEs.

The time to onset for each AE (relative to the first dose) will be calculated as follows for all TEAEs:

- Time to onset since first dose (Date of AE onset – Date of first dose of IMP).
- If the date of AE onset and date of first dose of IMP are the same, then the time to onset since first dose will be shown as <1 day.

In addition, the time to onset (in days) since the most recent dose prior to the TEAE will be calculated:

- Time to onset since most recent dose = (Date of AE onset – Date of most recent dose of IMP prior to the TEAE start) .

- If the date of AE onset and date of most recent dose of IMP prior to the TEAE start are the same, Time to onset since most recent dose will be shown as <1 day.
- The duration of each AE will be calculated as follows:
AE Duration (days) = (Date of outcome – date of onset)
- Imputations for missing start dates will be handled according to the 'Imputation of Partial Start Dates' rules in Section 4.3.5.
- Imputations for missing end dates will not be performed for classification as treatment emergent and for calculation of time to onset as this is not required.
- In the listings, where AE onset and end date are the same, AE duration will be presented as <1 day.
- For AEs with end date >onset date, the duration will be presented in days. For the calculation of duration for AEs with missing start dates, the dates will be imputed as described in Section 4.3.5.
- In case of uncoded AEs, these AEs should be designated as “UNCODED” at all MedDRA levels, and such AEs will be included in summary tables and participant listings based on this classification.
- All TEAEs will be flagged in the listings. In addition, all TEAEs will be summarized, but pre-treatment and post-treatment AEs will only be listed.
- The following summaries will be created:
 - (1) Incidence of treatment-emergent adverse events (TEAEs) by MedDRA system organ class, high level term, and preferred term
 - (2) Exposure adjusted incidence rate of TEAEs (incidence rate/event rate) to include the number of events, number and proportion of participants with the event (ie, incidence proportion), the exposure-adjusted incidence rate per 100 participant years with the associated 95% confidence interval, and the exposure adjusted event rate per 100 participant years.

For exposure adjusted incidence rate, the numerator will be the total number of participants experiencing the AE, each participant counted only once even if the participant has the event multiple times. The denominator will be in 100 participant-years. That is, the total summation of individual participant-years at risk up to the first occurrence of the TEAE for participants with that AE, and the total participant-years at risk for those participants not experiencing that AE, divided by 100. Incidence rates will be presented with a 95% confidence interval. Exact Poisson 95% CIs for incidence rates are calculated using the relationship between the Poisson and the Chi-square distribution (Ulm, 1990).

For exposure adjusted event rate, the numerator will be the number of AEs including repeat occurrences in individual participants. The denominator will be in 100 participant-years. That is, the total summation of individual participant-years at risk (total sum of "time at risk (last dose – first dose + 60)" for all participants) divided by 100. No confidence interval will be computed.

- (3) Incidence of Serious TEAEs
- (4) Incidence of serious TEAEs by relationship
- (5) Incidences of TEAEs by intensity, maximum intensity and by relationship at any time during the study
- (6) Incidence of TEAE of special interest (AESI)

Defined as any TEAE that a regulatory authority has mandated be reported on an expedited basis, regardless of the seriousness, expectedness, or relatedness of the AE to the administration of a UCB product/compound. For DZP, the following events require immediate reporting (within 24 hours regardless of seriousness) to UCB:

Hy's Law:

- Potential Hy's Law, defined as ≥ 3 xULN ALT or AST with coexisting ≥ 2 xULN total bilirubin in the absence of ≥ 2 xULN ALP, with no alternative explanation for the biochemical abnormality (ie, without waiting for any additional etiologic investigations to have been concluded). Follow-up information should be reported if an alternative etiology is identified during investigation and monitoring of the participant.
- Malignancies: haematological malignant tumours (SMQ), haematological tumours of unspecified malignancy (SMQ), non-haematological malignant tumours (SMQ) and non-haematological tumours of unspecified malignancy (SMQ).

- (7) Incidence of TEAE of special monitoring (AESM) as determined by the investigator. These are events of interest defined by the sponsor to be reported on an expedited basis to the sponsor, regardless of seriousness, expectedness, or relatedness of the AE to the administration of DZP
- (8) Incidence of TEAEs leading to temporary study drug discontinuation
- (9) Incidence of TEAEs leading to permanent study drug discontinuation or withdrawal from the study
- (10) Incidence of TEAEs occurring during treatment period (defined as last infusion + 28 days)
- (11) Incidence of opportunistic infection TEAEs (based on narrow SMQ for opportunistic infection)
- (12) Incidence of thromboembolic TEAEs (based on the “Emolic and thrombotic events” SMQ) (Note: this incidence table will be presented by maximum intensity)
- (13) Incidence of thromboembolic TEAEs as confirmed by the adjudication committee
- (14) Incidence of TEAEs fulfilling the definition of MACE, defined as events coded to MedDRA PTs under the narrow SMQ Central nervous system haemorrhages and cerebrovascular conditions, narrow SMQ Ischaemic heart disease, and narrow SMQ Cardiac failure, as well as the following additional MedDRA PTs: Cardiac death, Angioplasty, Arterial angioplasty, Atherosclerotic plaque rupture and Intra-aortic balloon placement

[figure not shown]
- (15) Incidence of TEAEs starting on the day or the day after an infusion.
- (16) Incidence of infusion reaction TEAEs in participants with infusion reactions (as indicated by the investigator on the CRF)
- (17) Incidence of infusion reactions meeting Sampson's criteria of Anaphylaxis as determined by the investigator
- (18) Incidence of TEAEs suggestive of [REDACTED] based on the narrow SMQ for [REDACTED]
- (19) Incidence of [REDACTED] TEAEs based on narrow SMQ for [REDACTED] starting on the day or the day after an infusion
- (20) Incidence of [REDACTED] TEAEs based on narrow SMQ for [REDACTED] starting later than the day after an infusion
- (21) Incidence of TEAEs in SMQ Anaphylactic reaction where scope='Narrow'
- (22) Incidence of TEAEs suggestive of suicidal events based on Suicide/self-injury (SMQ)
- (23) Incidence of TEAEs suggestive of depressive or suicidal events based on depression and suicide/self-injury (SMQ)
- (24) Incidence of TEAEs in the SMQ depression and suicide/self-injury where scope=narrow
- (25) Incidence of non-serious TEAEs occurring in $\geq 5\%$ of participants within any individual treatment group (incidence is compared to the threshold prior to any rounding)
- (26) Incidence of non-serious TEAEs by relationship
- (27) Incidence of TEAEs leading to permanent study drug discontinuation or withdraw from the study, by relationship
- (28) Incidence of fatal TEAEs by relationship
- (29) Incidence of TEAEs excluding adverse events related to COVID-19 vaccines as determined by the investigator
- (30) Incidence of TEAEs by Decreasing Incidence of MedDRA Preferred Term
- (31) Incidence of TEAEs Suggestive of Herpes Zoster TEAEs by Medication Subgroup

Figures:

- Relative Risk of Most Frequent AEs (Preferred Term) – All TEAEs
- Relative Risk of Most Frequent AEs (Higher Level Term) – All TEAEs

Note: most frequent will include top 30 most frequent TEAEs

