7.1 Discontinuation of study medication

Study participants who discontinue study medication will be encouraged to stay in the study under observation. They should continue to be followed for all regularly scheduled visits for safety and efficacy assessments.

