8.2.4 Clinical safety laboratory assessments

See Section 10.2 for the list of clinical laboratory tests to be performed. Some laboratory parameters may be subject to blinding. In case a blinded laboratory parameter is considered safety relevant, alert notifications in case of clinically significant levels or changes from baseline will be established.

Some immune system markers (Section 8.9) may also be considered safety markers.

The Investigator must review the laboratory report, document this review, and record the underlying disease or condition of clinically relevant laboratory changes occurring during the study or, in case an underlying disease or condition cannot be identified, the laboratory change itself in the AE section of the eCRF. The laboratory reports must be filed with the source documents. Clinically significant abnormal laboratory findings are those which are not associated with the underlying disease, unless judged by the Investigator to be more severe than expected for the participant's condition.

All laboratory tests with values considered clinically significantly abnormal during participation in the study or within 5 half-lives (10 Weeks) after the final dose of study medication should be repeated until the values return to normal or baseline or are no longer considered clinically significant by the Investigator or Medical Monitor.

If such values do not return to normal/Baseline within a period of time judged reasonable by the Investigator, the etiology should be identified and the Sponsor notified.

All protocol-required laboratory assessments, as defined in Section 10.2, must be conducted in accordance with the laboratory manual and the Schedule of Activities.

If laboratory values from non-protocol specified laboratory assessments performed at the institution's local laboratory require a change in participant management or are considered clinically significant by the Investigator (eg, SAE or AE or dose modification), then the results must be recorded in the eCRF.

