9.2.2 Analysis time points

The timeframe for this protocol compasses the entire study, which extends from Screening to 10 weeks after the final dose, ie, 48 weeks of Double-Blind Treatment Period and 6 weeks of SFU Period.

The following study periods will be included in the analysis:

- Screening Period: up to 14 days (Day -14 through Day -1).
- Double-Blind Treatment Period: 48 weeks, starts with the randomization (1:2) of eligible participants to 1 of 2 treatment arms (SOC+PBO or SOC+DZP 24mg/kg), stratified in accordance with the 3 stratification factors. Study medication will be administered by iv infusion every 4 weeks, starting on Day 1.
- Safety Follow-up Period: 6 weeks, participants who complete the 48-week Double-Blind Treatment Period will continue into this 6-week SFU Period. During this period, participants will not receive study medication but will be able to receive SOC treatment, as indicated.

The time points for individual assessments are provided in [Table 1-2](#).

Analyses conducted by visit will include each planned study visit at which the assessment was scheduled. Data for planned study visits will be based on the nominal time point and will not include any unplanned visits. Usually, efficacy data will not be obtained at unscheduled visits, with the following exceptions: labs in BILAG and SLEDAI-2K. Here labs that are obtained up to 2 weeks after the original visit are used to replace missing lab data.

Study participant data listings will include all time points for collected data, including all assessments (planned or unplanned). Data for derived time points Last Visit and Early Withdrawal will be included in study participant data listings.

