9.4 Planned safety and other analyses

9.4.1 Safety analyses

Safety variables will be analyzed for all study participants in the SS.

Adverse events will be coded according to the Medical Dictionary for Regulatory Activities (MedDRA®). The frequency of all AEs during the study period will be presented for each treatment group separately by System Organ Class, high level term, and preferred term. The data will be displayed as number of study participants experiencing the AEs, percentage of study participants, and number of AEs. Data will also be corrected for exposure and reported by 100 patient-years.

The incidence of study participants with AEs will be presented by treatment group and total treatment. Additional tables will summarize AEs leading to permanent discontinuation of study medication, AEs by maximum intensity, AEs by intensity, and AEs by relationship to study medication by treatment group and total treatment. Adverse events will be categorized by severity. The countermeasures taken for each AE, the time of onset of AEs after dosing, and AE duration will be listed. Additional tables with respect to all categories of AEs will also include the numbers of study participants who experienced the respective AE.

All TEAEs (serious and nonserious), including TEAEs of special interest, TEAEs of special monitoring, and deaths will also be tabulated and listed. Other laboratory safety parameters will also be tabulated and listed.

Laboratory evaluations, vital signs, and ECGs will be analyzed in the SS for observed cases. Descriptive statistics will be presented by treatment group at each time point: change from Baseline in vital signs, serum chemistry, hematology, and urinalysis. For laboratory data, changes between the Baseline (predose) or, if missing, Screening value and each posttreatment assessment may be presented in shift tables or using other summaries as detailed in the SAP.

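### SAP 10.1 only lists adverse events starting more than 60 days after the last dose, although protocol 9.4.1 promises all study-period events by treatment group

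*SAP*

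**What the plan says.** SAP 10.1 sets the window: "Treatment-emergent AEs are those with onset date on or after the first administration of study drug, and up to 60 days after last dose". It then gives the output rule: "all TEAEs will be summarized, but pre-treatment and post-treatment AEs will only be listed". The numbered summaries that follow in SAP 10.1 are all defined on TEAEs, apart from the one for infusion reactions meeting the Sampson criteria. They include the tables of serious events, events of special interest (with malignancies), opportunistic infections, thromboembolic events, MACE and fatal events.

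Protocol 9.4.1 is wider: "The frequency of all AEs during the study period will be presented for each treatment group separately by System Organ Class". A later sentence there, which opens with TEAEs, ends "TEAEs of special monitoring, and deaths will also be tabulated and listed". Protocol 9.2.2 describes the timeframe as one "which extends from Screening to 10 weeks after the final dose", and SAP 3.2 says the same. Protocol 8.3.1 collects AEs and SAEs from consent to the follow-up visit. For participants who stop study drug, protocol 7.1 says: "They should continue to be followed for all regularly scheduled visits for safety and efficacy assessments". Footnote a of the Schedule of Activities (protocol 1.3) waives the safety follow-up visit if drug was stopped more than 10 weeks before Week 48 and the Week 48 visit is attended. For such a participant Week 48 closes observation.

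The protocol describes five half-lives in two ways. The synopsis (Treatment groups and duration) ties them to more than 60 days after the Week 44 dose. Protocol 8.2.4 has "within 5 half-lives (10 Weeks) after the final dose of study medication".

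**The concern.** The protocol promises a by-arm presentation of all study-period adverse events, and the SAP delivers one of treatment-emergent events only. The readable part of SAP Table 3-1, where departures from protocol-defined analyses are recorded, does not mention it. SAP 10.1 is also incomplete in its own terms. It classifies events as either pre-treatment or treatment-emergent, then applies an output rule to a third class, post-treatment, that it never defines.

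At stake is what the between-arm safety comparison can show for events of late onset: malignancy, thromboembolism, serious infection and death. The participants most affected are those who stop drug early and stay in the study. Under protocol 7.1.3 permanent discontinuation is mandatory after, among other things, a thromboembolic event, drug-related anaphylaxis, drug-related potential liver injury, or active TB or NTM infection. Early stopping is therefore partly tied to safety problems. Whether later events in these participants differ between arms is unknown, and a listing gives no by-arm incidence.

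**Working it through.** **Inputs.** Schedule of Activities (protocol 1.3): Baseline Day 1, Week 4 Day 28, Week 12 Day 84, Week 24 Day 168, Week 36 Day 252, Week 40 Day 280, Week 44 (last planned dose) Day 308, Week 48 Day 336, Week 54 (safety follow-up) Day 378. TEAE window: last dose + 60 days (SAP 10.1).

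**Step 1: the plan's own figure.** 378 − 308 = 70 days = 10 weeks. This reproduces the 10-week follow-up in protocol 9.2.2 and SAP 3.2.

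**Step 2: days observed but outside every AE incidence table.**

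Untabulated days = (end of observation − last dose) − 60, with a floor of zero.

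End of observation is Day 336 when the last dose was more than 10 weeks earlier and the participant stays to Week 48. Otherwise it is last dose + 70.

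| Last dose | Window ends | Observed to | Untabulated days |
|---|---|---|---|
| Baseline, Day 1 | Day 61 | Day 336 | 275 |
| Week 4, Day 28 | Day 88 | Day 336 | 248 |
| Week 12, Day 84 | Day 144 | Day 336 | 192 |
| Week 24, Day 168 | Day 228 | Day 336 | 108 |
| Week 36, Day 252 | Day 312 | Day 336 | 24 |
| Week 40, Day 280 | Day 340 | Day 350 | 10 |
| Week 44, Day 308, no extension | Day 368 | Day 378 | 10 |
| Week 44, Day 308, enters extension | Day 368 | Day 336 | 0 |

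For completers who enter safety follow-up the share is 10/70 = 14% of post-dose days. Those entering the extension leave this study 336 − 308 = 28 days after the last dose, inside the window.

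**Step 3: do other outputs fill the gap?** The exposure-adjusted rates in SAP 10.1 use time at risk of last dose − first dose + 60, so they share the cut-off. The disposition and discontinuation-due-to-AE tables in SAP 5.1 may catch some late events or deaths but are not incidence tables. Laboratory, vital-sign and ECG summaries (SAP 10.3, 10.4.1, 10.4.2) use observed cases with all data included and no 60-day limit, so the gap concerns AE tables only.

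**Step 4: the two half-life statements.** 60/5 = 12 days and 70/5 = 14 days. The synopsis and protocol 8.2.4 therefore imply different half-lives.

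**The case against.** The best defence is that a 60-day window has a basis in the protocol synopsis, and that the protocol's safety endpoints are themselves TEAEs. Protocol section 9 also leaves detail to the SAP. This stands as far as the definition goes. A reader might infer that the window is an error and must become 70 days. The documents do not support that: they describe five half-lives in two ways, and choosing 70 days picks one side. The defence does not explain why nothing tabulates later events when 9.4.1 says study-period events will be presented.

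A reader might also infer that the protocol requires every study-period death to be tabulated. The sentence ending "TEAEs of special monitoring, and deaths will also be tabulated and listed" opens with TEAEs and can be read as deaths among them. The point rests on the all-AE sentence alone. Since the window is defined by onset, a late death from an event that began within it may still count as a fatal TEAE.

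Other objections carry some weight. An event that leads to stopping drug would ordinarily start inside the window, so only subsequent events are affected. Some of those will follow wash-out or a switch to other therapy, including a biologic (protocol 7.1.3, item 3), and mixing them with TEAEs would blur attribution. All AE data are still listed, so nothing is missing from the report. SAP Section 13 and the Amendment 3 rationale are redacted, so a supplementary table or declaration there cannot be excluded. The visible rule, "all TEAEs will be summarized, but pre-treatment and post-treatment AEs will only be listed", is nevertheless explicit.

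**Conclusion.** The concern holds as a gap in tabulation and an apparently undeclared narrowing of protocol 9.4.1. It is worth correcting before the tables are produced. The per-participant size is 24 to 275 untabulated days for someone whose last dose fell between Week 36 and Baseline and who stays to Day 336. It is 10 days for those entering safety follow-up and none for those entering the extension at Week 48.

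These figures assume visits on nominal days and, for early stoppers, attendance to Week 48. The documents give no discontinuation or retention rate, so no total in participant-years is offered. It would also be wrong to infer that safety data in general are lost, because only AE incidence tables and rates are affected.

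**What to change.** - Keep the 60-day TEAE tables as the main safety presentation.
- Define a post-treatment AE in SAP 10.1 (onset after the TEAE window), so that the classification and the output rule agree.
- Add one supportive by-arm table set covering deaths, SAEs, malignancies and thromboembolic events from first dose to end of study participation, regardless of time since last dose. Its time at risk should run to the same end point. Show it separately from the TEAE tables.
- Declare in SAP Table 3-1 any departure from protocol 9.4.1 that remains.
- Reconcile the two descriptions of five half-lives in the protocol synopsis and section 8.2.4.

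The cost is SAP wording and a few extra tables from data already collected. The downside is that some counted events will fall after wash-out or after a change of therapy, which is the reason for the separate presentation.

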	
 Seroconversion of: [REDACTED] [REDACTED] status by visit

 To evaluate the safety and tolerability of DZP as an add-on treatment to SOC medication 	
 TEAEs leading to study withdrawal, TEAEs leading to permanent study medication discontinuation, TEAEs with start day on day or up to 1 day after infusion, other identified TEAE clusters Summary of participants withdrawn from the study due to TEAEs

Objectives	Endpoints
	
Summary of participants who permanently discontinued study medicationChange from Baseline in vital sign parameters by visitObserved values and change from Baseline in safety laboratory tests (hematology, serum chemistry, urinalysis) by visit, % study participants achieving critical threshold for selected lab parameters by visits

To evaluate changes in exploratory biomarkers	
Change from Baseline in biomarkers selected for analysis

To evaluate risk for anti-phospholipid associated events	
Change from Baseline in APS score by visit

ACR/SLICC=American College of Rheumatology/Systemic Lupus International Collaborating Clinics; [REDACTED]; APS=antiphospholipid antibody syndrome; BICLA=BILAG 2004-based Composite Lupus Assessment; BILAG=British Isles Lupus Assessment Group Disease Activity Index 2004; CLASI=Cutaneous Lupus Erythematosus Disease Area and Severity Index; DORIS=definitions of remission in SLE; DZP=dapirolizumab pegol; [REDACTED]; EQ-5D-5L=Euro Quality of life 5-Dimensions 3-Level; Fab'=fragment antigen-binding; FACIT-F=Functional Assessment of Chronic Illness Therapy Fatigue; FATIGUE-PRO=Fatigue patient reported outcome; Ig=immunoglobulin; LLDAS=low lupus disease activity state; PD=pharmacodynamics; PEG=polyethylene glycol; PGA=Physician's Global Assessment of Disease; PHQ-9=Patient Health Questionnaire-9; PK=pharmacokinetic(s); SFI=SELENA Flare Index; SJC=swollen joint count; SLE=systemic lupus erythematosus; SLEDAI-2K=Systemic Lupus Erythematosus Disease Activity Index 2000; sm=Smith antigen; SOC=standard of care; SRI4, 6, 8=Systemic Lupus Erythematosus Responder Index-4, 6, 8; [REDACTED]; S2K RI50=Systemic Lupus Erythematosus Disease Activity Index-2000 Responder Index-50; TEAE=treatment-emergent adverse event; TJC=tender joint count

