- Achievement of LLDAS Variant (demand for \leq 5mg/day prednisone equivalent) in >50% of post-Baseline visits through Week 48
- Achievement of prednisone equivalent dose \leq 7.5mg/day by visit
- Prednisone equivalent dose by visit
- Occurrence of severe BILAG 2004 flares by visit
- Occurrence of moderate BILAG flares by visit
- Occurrence of severe SFI flares by visit
- Occurrence of moderate SFI flares by visit
- Time to severe SFI flare
- Time to moderate SFI flare
- Change from Baseline in American College of Rheumatology (ACR)/ Systemic Lupus International Collaborating Clinics (SLICC) damage score by visit
- Achievement of Definitions of Remission in SLE (DORIS) remission by visit
- Change from Baseline in Cutaneous Lupus Erythematosus Disease Area and Severity Index (CLASI) activity score by visit for all study participants and for subset of study participants with high CLASI score

- Achievement of a meaningful improvement in CLASI activity score by visit for all study participants and for subset of study participants with high CLASI score
- Change from Baseline in tender joint count (TJC) and swollen joint count (SJC) and tender and swollen joint count (T&SJC) by visit for all study participants and for subset of participants with moderate to severe [REDACTED]
- Achievement of a meaningful decrease in TJC/SJC by visit for all participants and for a subset of participants with moderate to severe [REDACTED]
- Change from Baseline in Lupus [REDACTED] and Musculoskeletal Disease Activity (LAMDA) score and it's components by visit
- Change from Baseline in Functional Assessment of Chronic Illness Therapy-Fatigue Scale (FACIT-F) by visit
- Change from Baseline in Patient Health Questionnaire-9 (PHQ-9) score by visit
- Change from Baseline in FATIGUE-PRO 'Physical Fatigue', 'Mental Fatigue' and 'Fatigability' scores by visit
- Change from Baseline in Lupus QoL by visit
- Change from Baseline in EQ-5D-5L by visit
- [REDACTED]
- [REDACTED]
- Incidence of anti-drug antibodies (ADA): [REDACTED]
- Observed values and change from Baseline in [REDACTED]
[REDACTED]
[REDACTED] in all study participants by visit and in study participants 'positive' at Baseline by visit
- Seroconversion of [REDACTED] status by visit
- TEAEs leading to study withdrawal, TEAEs leading to permanent study medication discontinuation, TEAEs with start day on day or up to 1 day after infusion, other identified TEAE clusters
- Summary of participants withdrawn from the study due to TEAEs

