- Summary of participants who permanently discontinued study medication
- Change from Baseline in vital sign parameters by visit
- Observed values and change from Baseline in safety laboratory tests (hematology, serum chemistry, urinalysis) by visit, % study participants achieving critical threshold for selected lab parameters by visits
- Change from Baseline in biomarkers selected for analysis

- [REDACTED]
- [REDACTED]
- Achievement of a meaningful improvement in CLASI activity sub score – erythema by visit for all study participants and for subset of study participants with high CLASI
- Achievement of a meaningful improvement in CLASI activity sub score – scaling by visit for all study participants and for subset of study participants with high CLASI
- Achievement of a meaningful improvement in CLASI activity sub score – alopecia by visit for all study participants and for subset of study participants with high CLASI

[figure not shown]

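### SAP 10.1 specifies TEAE incidence only for drug discontinuation and study withdrawal combined, although the protocol and SAP 2.2.4 list them as two endpoints

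*SAP*

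**What the plan says.** The tertiary safety endpoints, in the protocol (Tables 1-1 and 3-1) and again in SAP 2.2.4, name two items one after the other: "TEAEs leading to study withdrawal, TEAEs leading to permanent study medication discontinuation". Both documents also keep two participant-level summaries as further endpoints: "Summary of participants withdrawn from the study due to TEAEs" and "Summary of participants who permanently discontinued study medication".

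Protocol 9.4.1 then says: "Additional tables will summarize AEs leading to permanent discontinuation of study medication". Study withdrawal is not part of that table.

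The numbered outputs in SAP 10.1 join the two events. Summary (9) is "Incidence of TEAEs leading to permanent study drug discontinuation or withdrawal from the study". Summary (27) is "Incidence of TEAEs leading to permanent study drug discontinuation or withdraw from the study, by relationship".

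SAP 10.1 also says what is recorded for each AE. The action taken with study drug is one field. Later in the same list comes the "date of outcome and whether the AE led to study premature termination", so the effect on study participation is a field of its own.

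**The concern.** Stopping drug and leaving the study are different events in this trial. Protocol 7.1 says: "Study participants who discontinue study medication will be encouraged to stay in the study". Protocol 7.1.3 applies its permanent stopping rules to study drug and not necessarily to participation. Protocol 7.2 asks for withdrawal only when consent is withdrawn or when the IDMC, the ethics committee or a regulator requests it.

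A TEAE that ends treatment bears on tolerability. A TEAE that ends participation also ends follow-up, so it bears on how complete later safety and efficacy data are in each arm. A table that counts one or the other cannot show which happened. Taken as written, SAP 10.1 reports a different quantity from the two endpoints listed in SAP 2.2.4 and from the table promised in Protocol 9.4.1.

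**Working it through.** No rate, sample size or power figure is involved, so the check sets the texts side by side and adds one piece of set arithmetic.

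1. **Endpoints.** Protocol Tables 1-1 and 3-1 and SAP 2.2.4 all give two event-level items.
2. **Promised table.** Protocol 9.4.1 names permanent drug discontinuation only.
3. **Planned outputs.** Of summaries (1) to (31) in SAP 10.1, (8) covers temporary discontinuation, while (9) and (27) cover permanent discontinuation and withdrawal together. No other summary covers either event alone.
4. **Declared changes.** The readable rows of SAP Table 3-1 record tertiary-endpoint edits as small as replacing *at* with *through* before Week 48. They do not record this merge.
5. **Other outputs.** SAP 5.1 plans a disposition table with reasons, table (2), and a table of discontinuation because of an AE, table (4). Both use the Randomized Set, whereas SAP 10.1 uses the Safety Set. Table (4) does not say whether it means drug, study or both, is not restricted to treatment-emergent events, and has no stated layout. These two tables fit the participant-level endpoints more naturally than the event-level ones.
6. **Data.** The two per-AE fields in SAP 10.1 allow each event to be derived separately.

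**What the union can and cannot show.** Let *a* be the number of participants in an arm with a TEAE leading to permanent drug discontinuation, *b* the number with a TEAE leading to study withdrawal, and *u* the number with either. Then

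max(*a*, *b*) ≤ *u* ≤ *a* + *b*.

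In general neither *a* nor *b* can be recovered from *u*. If every AE-driven withdrawal is also a permanent drug discontinuation, then *b* is nested in *a*, so *u* = *a*. The union then equals the drug-discontinuation count, but *b* may lie anywhere from 0 to *u*.

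Nesting is likely to be close here. Someone who leaves the study before the last infusion at Week 44 receives no more drug. It can fail when withdrawal follows the last dose, when drug had already been stopped for another reason, or when the two eCRF fields are completed inconsistently.

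**The case against.** The strongest reply is that little is missing from the report as a whole. A reader might infer that the two endpoints and the promised table will not be produced at all. The documents do not support that reading. SAP 5.1 table (4) is devoted to AE-driven discontinuation, and its layout is not shown, so a breakdown by type or by MedDRA term cannot be excluded. SAP 10.1 says that all AE data will be listed with TEAEs flagged, so both fields should be visible for each event. The public SAP gives only titles, and a combined title does not rule out separate rows beneath it. Because withdrawal is largely nested in drug discontinuation, the combined table probably approximates the one promised in Protocol 9.4.1.

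The SAP also pairs the two events elsewhere: both lead to non-response for the primary endpoint, and SAP 5.1 plans one Kaplan-Meier plot of whichever comes first. That is a consistent convention for those purposes. It does not explain why two separately listed safety endpoints become one.

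All of this reduces the size of the point, but the gap in SAP 10.1 stays. Listings are not incidence summaries by arm. The SAP 5.1 table uses another analysis set and leaves its type of discontinuation undefined. Nothing in the readable text requires separate rows in (9) or (27). The nesting argument rescues the drug-discontinuation count, not the withdrawal count. The rationale for SAP Amendment 3, Section 13.19 and parts of Table 3-1 are redacted, and nothing is inferred from what they do not show.

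**Conclusion.** The point stands as a reporting gap. SAP 10.1 specifies TEAE incidence only for the union of two events that the protocol and SAP 2.2.4 list separately. It replaces the drug-discontinuation table of Protocol 9.4.1 with a combined one, without a readable note of the change. The main loss is an incidence summary of the TEAEs that ended study participation; the drug-discontinuation count is probably well approximated.

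The size is small: tertiary safety endpoints only, in two outputs. The primary and key secondary analyses, the testing strategy and the type I error rate are unaffected. No counts can be given from the documents, so how far *u* departs from *a* is unknown.

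The conclusion assumes that the output titles describe the table contents and that no redacted passage already specifies the split. The claim that the union lies close to drug discontinuation rests on the nesting argument and on consistent completion of the two eCRF fields.

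**What to change.** In SAP 10.1, present summaries (9) and (27) separately for TEAEs leading to permanent study drug discontinuation and TEAEs leading to withdrawal from the study, each by arm on the Safety Set. Separate tables or separate row blocks would both do. Derive them from the two fields already recorded for each AE, and keep the union as an overall row if wanted. In SAP 5.1, state whether table (4) reports discontinuation of drug, of study, or both.

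If the sponsor prefers the combined display alone, record it in SAP Table 3-1 as a departure from Protocol 9.4.1 and from the listed endpoints.

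The cost is two extra tables or row blocks and one clarifying sentence. No new data are needed, and the descriptive split has no multiplicity consequence.
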